	
follow-up only if clinically necessary. (see Medical and Surgical Interventions)
 
 • Orally-inhaled steroids for control of asthma will be permitted. • If infection is suspected at any time during the study, treatment with antibiotics will be permitted. • Use of monoclonal antibodies is prohibited throughout the 365-day follow-up period. • To the extent possible, subjects will be maintained on stable regimens of leukotriene inhibitors and/or immunotherapy for allergies, if currently on such regimens; however, use of breath-powered or other methods of intranasal steroid delivery for allergies is not permitted during the study. • Use of drug-eluting implants (PROPEL[®], PROPEL[®] Mini, PROPEL[®] Contour) is prohibited during the baseline procedure and throughout the 365-day follow-up unless placed immediately following repeat ESS performed in the operating room setting.

Medical and Surgical Interventions
	
Medical interventions:
 
 • During the study follow-up, high-dose steroids (e.g., oral, parenteral, injection, budesonide or other sinus steroid irrigations, rinses or drops, nebulized steroids administered nasally) may be used as a medical intervention in cases where a clinically significant increase or persistence in ethmoid sinus polyposis occurs, leading to subject seeking intervention. • High-dose steroids may be used for reasons other than ethmoid sinus obstruction, if medically necessary. • In either case, high-dose steroid interventions and reasons of their use will be recorded on the concomitant medication and follow-up case report forms (CRF). 
Surgical interventions:
 
 • During the study follow-up, surgical intervention (e.g., repeat ESS, office polypectomy) may be required in cases where a clinically significant increase or persistence in ethmoid sinus polyposis occurs.

Follow-up
	
Each subject will return for 7 follow-up visits:
 
 • Day 30 (± 7 days) • Day 60 (± 7 days) • Day 90 (± 7 days) implant removal & repeat placement • Day 120 (± 7 days) • Day 150 (± 7 days) • Day 180 (± 14 days) implant removal • Day 365 (± 14 days)

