10.2 Eligibility Criteria

To be enrolled in the study, patients must meet all of the following inclusion criteria and none of the following exclusion criteria.

Inclusion criteria

- a. Patient has provided written informed consent using a form approved by the reviewing institutional review board (IRB) and sponsor.
- b. Patient is ≥ 18 years of age.
- c. Patient is willing and able to comply with protocol requirements.
- d. Patient has a confirmed diagnosis of CS with nasal polyps, as defined in the 2016 “International Consensus Statement on Allergy and Rhinology”.
- e. Patient has undergone prior ESS including bilateral total ethmoidectomy at least 90 days prior to screening.
- f. Patient has evidence of bilateral ethmoid sinus obstruction due to polyposis warranting intervention (polyp grade ≥ 2 on each side).
- g. Patient is able to tolerate daily use of Mometasone Furoate Nasal Spray (MFNS).
- h. Patient is able to tolerate topical/local anesthesia.
- i. In the opinion of the investigator, patient’s ethmoid sinus anatomy is amenable to in-office bilateral placement of the S8 Sinus Implant (i.e., able to pass into the middle meatus on both sides the S8 Sinus Implant with 20 mm in nominal length and 7 mm in compressed diameter).
- j. Female patients of reproductive potential must not be pregnant or nursing and must agree to not become pregnant during their participation in the study.
- k. Female patients of childbearing potential must agree to use consistent and acceptable method(s) of birth control during their participation in the study.

Exclusion criteria

- a. Patient has extensive ethmoid sinus polyp grade (grade 4 on at least one side).
- b. Patient has extensive adhesions/synechiae (grade 3 or 4).

- c. Patient has used parenteral and injected steroids (e.g., Kenalog injection) during 30 days prior to the baseline procedure.
- d. Patient has used oral steroids, budesonide or other sinus steroid irrigations/rinses, nebulized steroids administered nasally or budesonide drops during 14 days prior to the baseline procedure.
- e. Patient has oral-steroid dependent condition such as chronic obstructive pulmonary disease (COPD) or asthma.
- f. Patient has known history of allergy or intolerance to corticosteroids or mometasone furoate.
- g. Patient has used monoclonal antibodies for asthma, allergies or nasal polyps (e.g., Dupixent, Nucala, Xolair) during 30 days prior to the baseline procedure.

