The crimper and delivery system must be disposed per standard institutional practices for biohazard waste. If the S8 Sinus Implant, delivery system or other system components are associated with a device-related adverse event (AE), malfunction or failure, all the components should be returned to sponsor for evaluation, when possible. For the return of biohazard product, sponsor must be contacted prior to product return for handling instructions.

Implant removal

The S8 Sinus Implant is made from bioabsorbable polymers designed to gradually soften over time. The implant may be left in the sinus to gradually release the corticosteroid over approximately 90 days. It must be removed by 90 days or may be removed earlier at the investigator's discretion, using standard surgical instruments. As the implant softens over time and the polyps decrease, the implant may expel out of the nose on its own or with actions such as sneezing or forceful nose blowing.

Implant malfunction

All potential implant malfunctions and any associated AEs will be recorded in the corresponding CRFs in the EDC system. All instances of suspected implant malfunction will be reviewed by the sponsor.

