11.3 Follow-Up Phase

The follow-up period begins immediately post-procedure (once the patient exits the clinic). Each subject will return for up to 7 follow-up visits (*see Section 5 Study Flow Diagram and Section 6 Schedule of Assessments*).

- Day 30 (\pm 7 days)
- Day 60 (\pm 7 days)
- Day 90 (\pm 7 days) – implant removal & repeat implant placement
- Day 120 (\pm 7 days)
- Day 150 (\pm 7 days)
- Day 180 (\pm 14 days) – implant removal, as applicable
- Day 365 (\pm 14 days)

The protocol-required follow-up assessment at each visit through Day 180 will consist of:

- Nasal obstruction/congestion questionnaire,
- SNOT-22 questionnaire, and
- Endoscopic grading and video recording.

Repeat implant placement procedure at Day 90

At the Day 90 follow-up visit, subjects with ethmoid sinuses with polyps (grade ≥ 1) will undergo repeat implant placement unilaterally or bilaterally. Repeat implant placement must not be performed in the ethmoid sinuses with no nasal polyps (grade < 1). All implants placed at Day 90 must be removed at Day 180 or may be removed earlier at the investigator's discretion.

If polypectomy is performed at the Day 90 follow-up visit, polyp grading must be done after polypectomy to qualify a given subject for repeat placement of the S8 Sinus Implant.

Note: The assessment of symptoms and pregnancy testing must be performed before repeat implant placement procedure.

Unscheduled visits

Subjects may come in for additional unscheduled office visits if necessary. Circumstances that may warrant additional visits include but are not limited to:

- Worsening of sinus symptoms,
- Sinus-related adverse events requiring medical evaluation, and/or
- Implant migration

The assessment at an unscheduled visit will consist of:

- Nasal obstruction/congestion questionnaire,
- SNOT-22 questionnaire, and
- Endoscopic grading and video recording.

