7.5 Safety Evaluation

Adverse events

All adverse events (AE) will be coded using the Medical Dictionary for Regulatory Activities (MedDRA). Where possible, and if applicable, AE will be localized to a sinus type and side.

The incidence and percentages of AE and serious adverse events (SAE) through Day 365, including treatment emergent AE (TEAE), implant-related AE and SAE, will be presented by MedDRA system organ class (SOC) and preferred term (PT). Complete patient listings of all adverse events will be provided. For each adverse event, the following will be specified:

- Start and stop dates, and event onset (study day)
- The affected side (right or left) if available
- Seriousness
- Severity
- Strength of relationship if available
- Action taken
- Outcome

In tables presenting implant-related AE, the incidences and percentages will also be presented based on two mutually exclusive periods of observation:

- from baseline to Day 90 (before repeat placement)
- from repeat placement (at Day 90) to Day 180

Concomitant medications

Prior and concomitant medications are coded to therapeutic class and PT using the World Health Organization (WHO) Drug Dictionary. All concomitant medications are listed and summarized in a table.

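### The two-period adverse event table in SAP 7.5 ignores whether an implant is still in place, so it cannot separate a difference in exposure from a difference in risk

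*SAP*

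**What the plan says.** The only objective (Protocol section 8, SAP 2.0) is the safety of repeat placement. There is one arm, so first and repeat use can be set against each other only within the study. The place where the SAP does this is section 7.5: for implant-related events, "the incidences and percentages will also be presented based on two mutually exclusive periods of observation". The first runs from baseline up to the repeat placement at Day 90; the second runs "from repeat placement (at Day 90) to Day 180".

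The visits that close the periods are listed in Protocol section 4 as "Day 90 (± 7 days) implant removal & repeat placement" and "Day 180 (± 14 days) implant removal". An implant need not stay until then. Protocol 11.2 and 11.3 allow earlier removal at the investigator's discretion in both courses, and 11.2 adds: "As the implant softens over time and the polyps decrease, the implant may expel out of the nose on its own".

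The two courses start from different polyp criteria. Entry (Protocol 10.2) reads "Patient has evidence of bilateral ethmoid sinus obstruction due to polyposis warranting intervention", with grade 2 or more on each side and grade 4 on either side excluded. At Day 90 (Protocol 11.3) the floor is grade 1 per sinus: "Repeat implant placement must not be performed in the ethmoid sinuses with no nasal polyps". Repeat placement may be on one side only, and grading follows any polypectomy done at that visit. No other procedure is allowed with the baseline placement (Protocol 11.2).

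Implant status (present, absent, removed) is summarised at Days 30 to 180. It is defined per sinus in SAP 4.3 but per subject in SAP 7.4, and it is not linked to adverse event onset or side. SAP 7.4 and 7.5 describe no time in place, no in-place flag and no exposure-based rate. SAP 5.0 defines the one analysis population by placement at baseline.

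**The concern.** A percentage of subjects with an event over a period depends on the risk while exposed and on how long exposure lasts. If implants from one course stay in for less time than those from the other, the two percentages will differ even when daily risk is the same. They may also agree when daily risk differs. A lower figure after repeat placement might then be read as reassurance when it reflects fewer days with an implant. A higher figure might be read as a signal when it reflects more days.

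The lower grade floor, possible polypectomy before grading, possible unilateral placement and discretionary removal are reasons to expect that exposure might not match between courses. Nothing planned would show the size of the mismatch next to the event percentages.

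**Working it through.** **1. The plan's own count.** SAP 7.2 and Protocol 16.1: 50 subjects × 2 sinuses = 100 implants at baseline; 100 + 85 = 185 procedures, which reproduces. Taking the stated ~90% directly gives 90 repeat implants and 190 procedures. This counts procedures. It says nothing about how long an implant stays in.

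**2. Length of the periods.** Day 90 has a window of ±7 days and Day 180 of ±14.
- First period: 90 − 7 = 83 to 90 + 7 = 97 days.
- Second period: (180 − 14) − (90 + 7) = 69 to (180 + 14) − (90 − 7) = 111 days.

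Both are centred on 90. The windows add spread but do not push in one direction.

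**3. Effect of unequal time in place.** The documents give no event rates and no times in place, so these inputs are assumptions: first-course incidence 20%, mean 75 days in place, constant hazard while in place, and the same daily hazard in both courses.
- Daily hazard: h = −ln(1 − 0.20)/75 = 0.00298.
- Repeat incidence at t days: 1 − exp(−h·t).
- If a share q of the hazard arises at the procedure and does not depend on time: 1 − exp(−75h·[q + (1 − q)·t/75]).

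| Mean days in place, repeat | q = 0 | q = 0.5 | q = 0.8 |
|---|---|---|---|
| 75 | 20.0% | 20.0% | 20.0% |
| 60 | 16.3% | 18.2% | 19.3% |
| 50 | 13.8% | 17.0% | 18.8% |
| 40 | 11.2% | 15.7% | 18.3% |

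With no procedural share, the apparent gain is 3.7, 6.2 or 8.8 points at 60, 50 or 40 days. With half procedural, it is 3.0 points at 50 days.

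**4. The same point in reverse.** With no procedural share, equal crude percentages would hide a repeat-course daily rate higher by 75/60 = 1.25, 75/50 = 1.5 or 75/40 = 1.88. If repeat implants stayed in longer, say 90 days, the repeat percentage would be 1 − exp(−90h) = 23.5% with no change in daily risk.

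**5. Denominator of the second period.** At 90% of sinuses, subjects with at least one repeat implant number 50 × 0.90 = 45 if the two sides always agree, and 50 × (1 − 0.10²) = 49.5 if they are independent. Keeping all 50 in the denominator multiplies the second-period percentage by 0.90 to 0.99. For example, 9 of 45 is 20.0%, but 9 of 50 is 18.0%.

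**6. Precision.** At the assumed 20%, 10 of 50 subjects have an event, with an exact 95% interval of 10.0% to 33.7%. The differences in step 3 are smaller than the sampling error of either percentage.

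**The case against.** The strongest reply is that the two periods are the two planned treatment courses. Each opens at a placement and closes at the visit scheduled for removal. Incidence per course as actually used, expulsions included, is a legitimate safety measure. The SAP presents the two periods side by side; it states no test, margin or hypothesis about them. Visit-level implant status and listings with onset day and side are already planned, so a careful reader could see whether retention differs. Relatedness covers drug, device and procedure (SAP 4.1), so an event can count after the implant is out. Protocol 15.3 lists risks of insertion and removal that do not grow with days in place.

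Much of this stands. It is why the existing table should be kept and why the illustration shrinks when part of the hazard is procedural. It does not close the gap: status is summarised apart from the events, SAP 7.4 has it at subject level, and no planned table gives time in place by course.

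A reader might go further and infer that repeat implants are expelled sooner, so that the table is biased toward making repeat use look safer. The documents do not support that:
- Protocol 11.2 and 15.4 say only that expulsion may occur as the implant softens and polyps decrease. They give no rate, no comparison by grade at placement and nothing specific to repeat implants.
- First-course implants start at grade 2 or more, so polyps there have at least as much room to decrease.
- The Day 90 floor is lower, but no ceiling is stated, whereas grade 4 is excluded at entry. Sinuses receiving a repeat implant may be less polypoid; this is not assured.
- The second period can be longer than the first as well as shorter.

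**Conclusion.** The point holds as a limit on interpretation. The period percentages do not account for time with an implant in place, and the plan offers no other result that does. A difference between first and repeat use, or the lack of one, could therefore come from exposure, from risk or from both.

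The direction is unknown. Shorter retention after repeat placement is an inference, not something the protocol states. The size is also unknown. On the assumed inputs the artefact runs from 3.7 to 8.8 points with no procedural events and is about 3.0 points at 50 days with half the hazard procedural. It vanishes if time in place is equal or if all events are procedural. These figures rest on an assumed 20% incidence, assumed days in place and a constant hazard.

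This is a worthwhile, inexpensive addition to the SAP. It does not show that the planned table is wrong as a description of events per course. The table and listing mock-ups (SAP Appendices B and C) are not shown in the public text, so this verdict rests on the wording of SAP 7.4 and 7.5.

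**What to change.** Keep the two-period table, and add the following to SAP 7.5 before database lock.

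- **Time in place.** Derive it per sinus for first and repeat implants: placement to removal date, or to the midpoint between the last visit with status present and the first with status absent. Use the per-sinus implant status of SAP 4.3, and bring the per-subject wording in SAP 7.4 into line. Summarise by course.
- **Onset flag.** Mark each implant-related event as starting with or without an implant in place. Use the affected side where recorded; otherwise classify at subject level, as in place if either side holds an implant.
- **Supportive rate.** Report events per 1,000 implant-days by course, descriptively. Report events on placement and removal days per procedure, not per day. Removal of the first implant and placement of the second can both fall on the Day 90 visit, so state how an event on that day is assigned.
- **Denominator.** For the second period, use subjects and sinuses that received a repeat implant, and print both numbers.

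The cost is SAP wording and one added table, with no new visits or subjects. The inputs are visit-level implant status and adverse event onset and side, which are planned, plus removal dates; the documents do not say whether the removal date is a recorded field, so this should be confirmed. Expulsion dates will be known only to the visit interval, side will be missing for some events, and the rates will rest on few events, so they should be read as descriptive.

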8.0 APPENDICES

Appendix A: Schedule of Assessments

Assessment	Screening	Baseline/Procedure	Day 30 (\pm 7 days)	Day 60 (\pm 7 days)	Day 90 (\pm 7 days)	Day 120 (\pm 7 days)	Day 150 (\pm 7 days)	Day 180 (\pm 14 days)	Day 365 (\pm 14 days)
Informed consent	X								
Medical/surgical history	X								
Endoscopic grading & recording	X	X	X	X	X	X	X	X	
Nasal Obstruction/Congestion		X	X	X	X	X	X	X	
Sino-Nasal Outcome Test (SNOT-22)		X	X	X	X	X	X	X	
In-office implant placement (bilateral)		X							
Implant removal					X			X	
In-office repeat placement (unilateral or bilateral)					X ^a				
Concomitant medications	X	X	X	X	X	X	X	X	X
Adverse events reporting	X	X	X	X	X	X	X	X	X
Pregnancy test (female subjects)	X ^b	X ^b			X ^b				
Documented birth control (female subjects)		X ^c	X	X	X	X	X	X	X

Note: If screening and baseline/procedure visits occur on the same day, assessments must be recorded on the baseline visit forms.

- ^{a.} Repeat implant placement is performed at Day 90 in each ethmoid sinus with polyp grade \geq 1.
- ^{b.} Female subjects with reproductive potential are required to undergo a urine pregnancy test at screening and prior to the baseline procedure. If the screening and baseline/procedure visits occur on the same day, only one urine pregnancy test is required prior to the baseline procedure. The pregnancy test must be repeated at Day 90 prior to repeat implant placement procedure.
- ^{c.} Female subjects are required to confirm their nursing status at baseline.

Appendix B: Table Mock-Ups

Appendix C: Listing Mock-Ups
